Management of Sub-Clinical Bacteriuria in Pregnancy: A Feasibility Trial

NCT03275623

Version Date: 08/22/2017

Management of Sub-Clinical Bacteriuria in Pregnancy: A Feasibility Trial

[name]
[name]
[name]
[name]

Background:

Bacterial Colonization in the Urine

Assessment and treatment of bacterial colonization in the urine during pregnancy is a routine part of prenatal care.¹ A urinary tract infection (**UTI**) is defined as urine culture colonization >100,000 (**10⁵**) colony forming units (**CFU**) of bacteria per ml with signs and symptoms of UTI including dysuria, frequency, urgency, suprapubic pain, and/or hematuria.¹⁻³ Asymptomatic bacteriuria (**ASB**) is defined as urine culture colonization > 10⁵ CFU in the absence of signs and symptoms of UTI, and occurs in 2-10% of pregnancies.^{3,4} Pregnant women with a UTI or ASB are routinely prescribed antimicrobial therapy based on identified organisms and sensitivities.

Sub-Clinical Bacteriuria

Sub-clinical bacteriuria (**SCB**) occurs when urine culture colonization is between 1 - 10⁵ CFU. The frequency by which SCB occurs in pregnancy is unknown. It is also unknown the rate of progression from SCB to UTI and/or ASB, and subsequently development in to pyelonephritis. Moreover, there are no current guidelines that direct management in this particular condition in pregnancy. In current clinical practice, there is strong variation in care such that many patients are treated, despite the lack of proven benefit while other clinicians do not treat.

[figure not shown]

Figure 1. Schematic of potential progression of bacterial colonization in the urine.

Clinical Importance

Bacterial colonization in the urine during pregnancy can lead to adverse maternal and neonatal outcomes. Pyelonephritis is the primary concern in pregnancy due to its association with potential urosepsis, renal abscess, decline in renal function, preterm labor and preterm birth.⁵ Although untreated

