The gap in knowledge is whether the risks and benefits of empiric treatment with antimicrobial therapy for treatment of SCB outweigh the risk and benefits of developing UTI, ASB or pyelonephritis from expectant management or no treatment of SCB.

Rationale for this clinical trial

The rationale for this clinical trial is to determine if treatment of urine cultures with organisms of 1 – 100,000 CFU are beneficial to pregnancy outcomes when obtained at routine prenatal clinic visits. In current clinical practice, there is a strong variation in care such that many patients are treated for urine cultures with organisms of $<10^5$ CFU despite the lack of proven benefit while other clinicians do not treat.

If it is found that treatment of urine cultures with 1 - 10^5 CFU impact clinical care of a pregnant patient by decreasing adverse pregnancy outcome, guidelines will need to be modified to include treatment recommendations of urine cultures that do not currently meet criteria of a urinary tract infection. On the other hand, if there is no benefit to treatment of urine cultures 1 - 10^5 CFU, then unnecessary antibiotics could be avoided thereby potentially reducing unknown adverse effects to these drugs or resistance to antibiotics, which continues to be an alarming health challenge.

Hypothesis:

We hypothesize that treating urine cultures with organisms between 1- 10^5 CFU grown in culture media in a pregnant population leads to improvement of pregnancy outcomes.

Objectives:

To determine the rate of progression from SCB to either UTI or ASB with antimicrobial treatment of urine cultures with organisms of $1-10^5$ CFU compared to no treatment at prenatal care clinic visits.

Study Design:

For this pilot study, we propose a feasibility trial to determine if a randomized control trial for the treatment of subclinical cystitis to prevent pyelonephritis and culture proven cystitis. The trial will investigate the effects of treatment or non-treatment of urine cultures obtained during prenatal care visits prompted by a positive urinalysis or symptoms, and determine if a randomized control trial is needed to further investigate outcomes.

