Because this is a feasibility trial, 50 patients will be recruited from all clinical sites. 25 patients will be randomized to prenatal care with treatment for any urine culture with growth between $1-10^5$ CFU of any organism and 25 patients will be randomized to prenatal care without treatment for any urine culture with growth between $1-10^5$ CFU of any organism. Recruitment will be stopped after recruitment of 50 randomized patients or a 10-month time period whichever is completed first.

Data Analysis

Chi-square tests will be used to compare categorical data between the two treatment groups. Student's t-test will be used to compare numerical data. The rate of progression to SCB, UTI, or pyelonephritis will be determined by clinical findings, diagnosis if admitted to the hospital and laboratory/urine culture results meeting criteria for those mentioned above.

Procedures to Maintain Confidentiality

All information and data will be kept on paper research charts that will be stored in a locked file cabinet within a locked research office of our research team/research coordinator. In addition, an electronic database of information and data will be stored on the computer of our research coordinator that is password protected, and in a locked office of the research coordinator. We will record subject information only by study code number.

Potential Benefits and Risks

There are potential risks and benefits to either treatment strategy. Since treatment or no treatment are currently both generally accepted standard of care options, providers, based on their personal preference and practice style, may choose to treat or not. Potential benefits of antibiotic treatment of those with $1-10^5$ CFU in urine culture may be decreased development of UTI, pyelonephritis, PTL, and preterm birth. Potential risks of treatment may be side effects of the medications as well as potential untoward effects of antibiotic therapy that may increase development of resistant organisms in urine and other locations (e.g. vaginal, cervix, gut) or may lead to change in flora (e.g. vaginal, cervix, gut) which may increase risk of adverse pregnancy outcomes. The benefits of no treatment may be to avoid unnecessary and unindicated antibiotic therapy. If evidence shows that treatment of this subset of

pregnant patients decreases adverse pregnancy outcome, this can leave a lasting impact on how we treat urinary tract infections in pregnancy.

References

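### Data Analysis lists SCB, the state in which women are randomised, as a progression endpoint and omits ASB, so it matches neither the Objective nor the Primary Outcome

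*Combined protocol and SAP*

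**What the plan says.** The Data Analysis section of the combined protocol and SAP describes the progression endpoint as follows: "The rate of progression to SCB, UTI, or pyelonephritis will be determined by clinical findings". Besides clinical findings and hospital diagnosis, it relies on "laboratory/urine culture results meeting criteria for those mentioned above".

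The definitions are in the Background. SCB "occurs when urine culture colonization is between 1 - 10⁵ CFU". ASB "is defined as urine culture colonization > 10⁵ CFU in the absence of signs and symptoms of UTI". UTI has the same threshold but requires symptoms: above 10^5 CFU "of bacteria per ml with signs and symptoms of UTI including dysuria, frequency, urgency, suprapubic pain, and/or hematuria".

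The section on the randomised groups and the Methods section both randomise women on a culture of 1-10^5 CFU, and the Exclusion Criteria remove women whose culture is above 10^5 CFU. Every woman therefore enters the comparison with SCB.

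The Objective is "To determine the rate of progression from SCB to either UTI or ASB with antimicrobial treatment of urine cultures". The Primary Outcome is cystitis, defined as any culture above 10^5 during antenatal care with no symptom condition, together with the incidence of pyelonephritis.

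**The concern.** A woman whose later culture is still 1-10^5 CFU has not progressed. One who clears and then returns to that range has recurred, which is not the progression the Objective describes. The Data Analysis sentence nevertheless lists SCB as an end state and does not list ASB, one of the Objective's two end states.

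The same sentence ties the rate to cultures that meet the criteria of the named conditions. Under the Background definitions, a follow-up culture of 1-10^5 CFU meets the SCB criterion and would be counted. An asymptomatic culture above 10^5 CFU meets none of the three: it is above the SCB range, UTI needs symptoms, and it is not pyelonephritis.

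Both results can occur in this trial. Methods calls for test-of-cure cultures that do not depend on symptoms, and Study Design allows a culture on a positive urinalysis alone. The reported progression rate, which is the Objective, could then contradict the Primary Outcome computed from the same women.

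**Working it through.** The plan gives no figure to reproduce here, so the check sets the endpoint statements side by side.

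**Step 1: classify each follow-up state.** The five states below are a device for comparison, built from the Background definitions. 1 means counted as an event, 0 not counted.

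| Follow-up state | Data Analysis as written | Objective | Primary Outcome | Data Analysis with ASB for SCB |
|---|---|---|---|---|
| Negative culture | 0 | 0 | 0 | 0 |
| 1-10^5 CFU (SCB) | 1 | 0 | 0 | 0 |
| >10^5 CFU, no symptoms (ASB) | 0 | 1 | 1 | 1 |
| >10^5 CFU, symptoms (UTI) | 1 | 1 | 1 | 1 |
| Pyelonephritis | 1 | 0 | 1 | 1 |

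**Step 2: count the rows that differ.**

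- As written v Primary Outcome: SCB and ASB, 2 of 5.
- As written v Objective: SCB, ASB and pyelonephritis, 3 of 5.
- Corrected v Primary Outcome: 0 of 5.
- Corrected v Objective: pyelonephritis, 1 of 5.

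Replacing one label removes every disagreement with the Primary Outcome. The remaining difference from the Objective is a separate gap: the Objective does not mention pyelonephritis and the Primary Outcome does.

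**Step 3: is it a slip?** Five statements of progression in the text name ASB or SCB as an end state.

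- Background, Sub-Clinical Bacteriuria: ASB. "It is also unknown the rate of progression from SCB to UTI and/or ASB, and subsequently development in to pyelonephritis"
- Gap in Knowledge: ASB. "developing UTI, ASB or pyelonephritis from expectant management or no treatment of SCB"
- Objectives: ASB, as quoted above.
- Background, Clinical Importance: SCB, paired with UTI, in a sentence about how SCB itself progresses.
- Data Analysis: SCB.

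Three say ASB and two say SCB. Gap in Knowledge has the same three-item list as Data Analysis, with ASB where Data Analysis has SCB. That makes a slip much the likeliest explanation, though it remains an inference. Figure 1, the schematic of progression, is not reproduced in the text available and could not be checked.

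**The case against.** The strongest reply is that this is an editorial error with little consequence. The Primary Outcome is fixed independently of it, and harm arises only if an analyst follows the Data Analysis sentence literally. That is largely right, and it is why the point is minor.

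Three narrower objections concern the literal reading:

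- **The word progression may itself exclude women who stay at 1-10^5 CFU.** If so, the SCB row becomes 0, but ASB is still left out and 1 of 5 states still differs from the Primary Outcome.
- **The protocol sometimes uses UTI or cystitis by threshold alone**, so UTI might be taken to include asymptomatic cultures above 10^5 CFU. On that reading the ASB row becomes 1, but SCB is still counted and again 1 of 5 differs. The Background's explicit symptom requirement is the better guide. Only if this and the previous reading are both adopted does the mismatch with the Primary Outcome vanish, and then listing SCB has no effect.
- **The Background pathway runs through UTI or ASB to pyelonephritis**, so a woman with pyelonephritis might already count under the Objective. The counts against the Objective would then be 2 of 5 as written and 0 of 5 when corrected. The 3 and 1 above follow the Objective's literal wording. The counts against the Primary Outcome do not change.

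None of these removes the error. Each shows that the sentence needs a generous reading to agree with the rest of the plan.

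**Conclusion.** The concern holds, as a minor one. The sentence that defines how the progression rate is determined names the baseline state as an end state and omits ASB. On the Background definitions and the literal wording, it disagrees with the Primary Outcome in 2 of 5 follow-up states and with the Objective in 3 of 5.

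These are counts of categories, not of women. The documents call the progression rate unknown and give no rate at which SCB persists, so the number of women who would be misclassified cannot be estimated. The sample size is unaffected. The effect is confined to the progression rate, because the Primary Outcome would still record every culture above 10^5 CFU and every case of pyelonephritis.

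**What to change.** - **Data Analysis:** define progression as ASB or UTI (any culture above 10^5 CFU after randomisation, as in the Primary Outcome) or pyelonephritis. State that growth of 1-10^5 CFU after randomisation is not progression.
- **Background, Clinical Importance:** replace SCB with ASB as the end state. This is clerical.
- **Objectives:** bring the endpoint wording into line with the Primary Outcome, which includes pyelonephritis.

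The cost is a few words of protocol text, with no change to the primary endpoint data.
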